**Table 3 Overview of Planned Outputs to Describe the Association Between Selected Pairs of Parameters at Final analysis.**

Paired Variables	Data Type				Time points	Additional covariates in statistical models		
	X-variable		Y-variable					
	Absolute	Change	Absolute	Change				
X=mHTT, Y=Clinical Endpoints §	Y		Y		X & Y=BSL	BSL-Age, CAG, CAP, Country		
	Y			Y	X=BSL, Y=15M	BSL- Clin.endp, BSL-Age, CAG, CAP, Country		
		Y		Y	X=3M, 9M, 15M, Y=15M	BSL- Clin.endp, BSL-mHTT, BSL-Age, CAG, CAP, Country		
X= CSF Biomarkers, Y=Clinical Endpoints	Y		Y		X & Y=BSL	BSL-Age, CAG, CAP, Country		
	Y			Y	X=BSL, Y=15M	BSL- Clin.endp, BSL-Age, CAG, CAP, Country		
		Y		Y	X=3M, 9M, 15M, Y=15M	BSL- Clin.endp, BSL-CSF.Biom, BSL-Age, CAG, CAP, Country		
X=mHTT, Y=CSF Biomarkers *	Y		Y		X & Y=BSL	BSL-Age, CAG, CAP		
	Y			Y	X=BSL, Y=15M	BSL- CSF.Biom, BSL-Age, CAG, CAP		
		Y		Y	X & Y=3M, 9M, 15M	BSL-CSF.Biom, BSL-mHTT, BSL-Age, CAG, CAP		
X=CSF-NfL, Y=Plasma-NfL	Y		Y		X & Y=BSL	None		
		Y		Y	X & Y=3M, 9M, 15M	None		
X=mHTT, Y=normalised MRI	Y		Y		X & Y=BSL	BSL-Age, CAG, CAP		
X=CSF-Biom Y=normalised MRI	Y		Y		X & Y=BSL	BSL-Age, CAG, CAP		
X=mHTT, Y=BSI *	Y			Y (%-change)	X=BSL, Y=3M, 9M, 15M	BSL-Age, CAG, CAP		
		Y		Y (%-change)	X=3M, 9M, 15M, Y=15M	BSL-mHTT, BSL-Age, CAG, CAP		
X=CSF-Biom, Y=BSI *		Y		Y (%-change)	X=3M, 9M, 15M, Y=15M	BSL-Biom, BSL-Age, CAG, CAP		

**Table 3 Overview of Planned Outputs to Describe the Association Between Selected Pairs of Parameters at Final analysis (cont.)**

BSL= baseline; BSI= boundary shift integral; mHTT=mutant huntingtin protein; CAP= =(CAG-33.66)\* AGE\_BASELINE; CSF= cerebrospinal fluid; NfL= neurofilament light chain; MRI= magnetic resonance imaging.

§ Clinical Endpoints will include cUHDRS, TFC, TMS, SDMT and SWR

+ CSF Biomarkers will include NFL, YKL-40 and Tau

‡ MRI Volume

\* BSI is already a measure of change thus the change is not derived.

In case of an interim analysis (see Section 4.9) the analyses will be based on the available data (e.g. up to 9 months) by the clinical cutoff date.

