6.3 PRIMARY ANALYSES

The primary objective of this study is to investigate whether baseline CSF mHTT is a predictor of the change from baseline to 15 months for the following variables:

- Clinical endpoints (cUHDRS, TFC, TMS, SDMT, SWR, and IS)
- CSF and blood biomarkers
- Brain imaging (MRI)

Initially, a linear model will be used to evaluate the association between each response variable (e.g., change from baseline to 15 months in cUHDRS) and baseline CSF mHTT without adjustment for any baseline characteristics.

The same model will then be considered again, adjusting for baseline level of the response variable (e.g., baseline cUHDRS), baseline CSF mHTT levels, CAG, and baseline CAP (the latter defined as the product of age at baseline by [CAG—33.66] (Zhang et al. 2011). A sensitivity analysis to evaluate the impact of additional baseline characteristics (e.g., gender, education level) may be performed.

Other approaches may be used in the case of severe multicollinearity, which would result in model instability.

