### **4.3.1 Montreal Cognitive Assessment**

The Montreal Cognitive Assessment is an 11-item clinician-reported assessment that is used to detect cognitive impairment. It contains a series of basic assessments, including attention and visuospatial tasks. The total score ranges from 0–30, where lower scores indicate greater impairment. A scoring  $\geq 26/30$  is considered normal. This assessment is only conducted at screening. Individual items contributing to the total score are listed below:

- Visuospatial /executive (0 to 5)
- Naming (0 to 3)
- Attention (0 to 6)
- Language (0 to 3)
- Abstraction (0 to 2)
- Delayed recall (0 to 5)
- Orientation (0 to 6)

The total score is given by the sum of all sub scores; one point will be added by the assessor for subject who has 12 years or fewer of formal education, for a possible maximum of 30 points.

Missing values will not be imputed and total score derived only if all items are present. The assessment is considered completed if there are no missing items.

Descriptive summaries of the baseline values will be provided for the overall score (as continuous variable).

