#### **4.5.1.3.4 Stroop Word Reading Test**

The Stroop Word Reading Test (SWRT) is a measure of processing and psychomotor speed. Patients are presented with a page of color names printed in black ink and are asked to read aloud as many words as possible within a given amount of time (45 seconds in Study BN40422). The number of words read correctly is counted and higher scores indicate better cognitive performance. The raw score will be used for the analysis.

The scale is not considered completed if there is no result available. There will be no imputation for missing data even if the patient is not able or refuses to complete the task.

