##### **4.5.2.2 Model-based Analyses**

In order to model the relationship between a continuous response variable (e.g. the change in cUHDRS) and a main predictor (e.g. change in CSF mHTT) at a given time-point, a linear regression model (LRM) will be used. At each time point only those data from visit occurring  $\pm$  56 days from the scheduled visit will be used.

The full list of analyses which will be considered, together with specifications about additional covariates to account for, is provided in [Table 3](#). Additional analyses, not listed in this SAP, may be conducted to better understand any safety concern which may arise.

Least squares means (LSM) estimates, at each time-point, for the slope of the main predictor (X-variable in [Table 3](#)) along with corresponding standard error, 95% CI and unadjusted p-value will be presented. The estimated effect represents the effect of the main predictor on the response adjusted for all other covariates in the model. Distributional assumptions underlying the model used for analysis will be examined to gain confidence that the model assumptions are reasonable and where needed, sensitivity analyses will be performed.

The procedure that will be used to fit linear regression in SAS is as follows:

```
proc mixed data=dataname plots=all;
class
model y-variable= x-variable + {additional covariates in Table 3} /ddfmi=kr cl;
ods output solutionf=outputname;
run;
```

In addition to [Table 3](#), scatter plots and Spearman correlations will be calculated among all baseline fluid biomarkers at baseline. Similar analyses will be performed for CAG and CAP with baseline fluid biomarkers, baseline CSF mHTT and baseline cUHDRS (including individual components). CAP is defined by the product of (CAG – 33.66) by baseline age.

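### The baseline-on-baseline rows of SAP Table 3 for SDMT, SWR and cUHDRS leave out education, which is collected and has no baseline score to stand in for it

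*SAP*

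**What the plan says.** SAP 4.5.2.2 presents Table 3 as complete: "The full list of analyses which will be considered, together with specifications about additional covariates to account for, is provided in" that table. The endpoints covered are listed in its footnote: "Clinical Endpoints will include cUHDRS, TFC, TMS, SDMT and SWR".

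The covariates for the clinical-endpoint rows are:

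- **Baseline on baseline** (X & Y=BSL), for X=mHTT and again for X=CSF biomarkers: "BSL-Age, CAG, CAP, Country".
- **Baseline predictor, 15-month change**: "BSL- Clin.endp, BSL-Age, CAG, CAP, Country".
- **Change on change, mHTT**: "BSL- Clin.endp, BSL-mHTT, BSL-Age, CAG, CAP, Country". The CSF-biomarker row has the same form.

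No row of the table contains education or sex. Both are collected (Protocol 4.5.3, with education on the ISCED scale), and both are summarised descriptively at baseline (SAP 4.3).

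Protocol 6.3 says of the adjusted primary model: "A sensitivity analysis to evaluate the impact of additional baseline characteristics (e.g., gender, education level) may be performed". Protocol 6.4 says much the same for the secondary models. The synopsis reproduced in SAP Appendix 1 repeats the primary-analysis option, but SAP Section 4 does not specify it. The sensitivity analyses mentioned in SAP 4.5.2.2 concern distributional assumptions and name no covariates.

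For SWR the SAP states: "The raw score will be used for the analysis". SAP 4.5.1.3.5 builds cUHDRS from raw totals. For the MoCA, by contrast, "one point will be added by the assessor for subject who has 12 years or fewer of formal education" (SAP 4.3.1).

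**The concern.** Timed symbol-matching and word-reading scores may differ with schooling for reasons unrelated to Huntington's disease. In a change model with the baseline score as a covariate, a stable difference of that kind is largely removed. In a baseline-on-baseline model the score is the response, and nothing else in the covariate list is a direct measure of schooling.

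Two things follow. Education-related variance goes into the residual and widens the interval for the slope. If education is also correlated with the biomarker, by chance or in truth, the slope itself moves. The models exposed are 4 predictors (mHTT, NfL, tau, YKL-40) × 3 endpoints (SDMT, SWR, cUHDRS) = 12. At stake are the precision and credibility of the cross-sectional associations.

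**Working it through.** The plan gives no figure for the effect of education and no precision calculation, so there is nothing of its own to reproduce.

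**Inputs**
- n = 2 × 46 = 92, from the 2:1 match in SAP 2.3. The text allows up to approximately 100.
- Base model: intercept, predictor, age, CAG, CAP and country. With 6 countries (assumed) that is 5 + 5 = 10 parameters, leaving 82 residual df.
- Education explains a share R² of the variance left after those terms. The documents give no value, so 5-20% is assumed.

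**Precision in the baseline rows, one ordered education term (1 df)**

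SE ratio (adjusted / unadjusted) = √[(1 − R²) × 82/81], with education uncorrelated with the predictor.

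| R² | Calculation | SE ratio | Change in SE |
|---|---|---|---|
| 0 | √(1.0123) | 1.006 | +0.6% |
| 5% | √(0.95 × 1.0123) | 0.981 | −1.9% |
| 10% | √(0.90 × 1.0123) | 0.955 | −4.5% |
| 20% | √(0.80 × 1.0123) | 0.900 | −10.0% |

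**Cost if education is unrelated to the score but correlates 0.2 with the predictor** (assumed): 1.006 / √(1 − 0.2²) = 1.006 / √0.96 = 1.027, about 3% wider.

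**Cost of a larger adjustment.** Education in three categories plus sex uses 3 df. With no effect, √(82/79) = 1.019, about 2% wider before any collinearity.

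**Shift of the slope in the baseline rows.** Take a standardised score, a predictor that explains 10% of it (slope −√0.10 = −0.316), education that explains 10% (coefficient √0.10 = 0.316), and a correlation of 0.2 between the two. Without education the slope is −0.316 + 0.2 × 0.316 = −0.253. That is one fifth closer to zero; with the opposite sign of correlation it would be exaggerated by the same amount. A large simulation (400,000 records) gave −0.253 without education and −0.317 with it. If the true correlation is zero, a sample correlation of 0.2 or more in either direction occurs in roughly 6% of samples of 92, and one of 0.1 or more in roughly a third.

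**Change rows.** The same simulation added a follow-up score in which education shifts both visits equally and does not affect true change. Education explained 5-20% of the score and reliability was 0.80-0.95 (both assumed). With the baseline score in the model, the partial R² left for education was 0.001-0.029. Leaving education out inflates the SE by 1/√(1 − 0.001) = 1.0005 to 1/√(1 − 0.029) = 1.015, so by about 0-1.5%. At a correlation of 0.2, education R² of 10% and reliability 0.90, the slope moved from −0.127 to −0.139. That is a shift of 0.012, against 0.064 in the baseline row.

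**The case against.** **The SAP has dropped something the protocol promised.** A reader might infer this, but the documents do not support it. The protocol gives gender and education only as examples in an optional sensitivity analysis. Its own adjusted model has the baseline response, baseline mHTT, CAG and CAP. Table 3 already goes further by adding age and country.

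**All mHTT and biomarker slopes for these endpoints are affected.** This is also tempting and also too strong. Every clinical-endpoint change row contains the baseline score, and the loss of precision there is 1.5% at most under the assumptions above. The stated primary and secondary objectives rest on the change rows, not on the baseline-on-baseline rows.

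**The SAP closes the door on the check.** It does not. SAP Appendix 1 repeats the option, SAP Section 1 lets the SAP override the protocol only where it specifies something, and SAP 4.5.3 allows further exploratory analyses. What is missing is a plan made in advance.

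**The MoCA point shows that the SAP regards SDMT and SWR as needing correction.** It shows less than that. The point belongs to the scoring of that instrument and is added by the assessor, for a measure taken only at screening. It makes an effect of schooling on cognitive scores plausible and no more.

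**The size is assumed, and a short covariate list is defensible.** Both parts stand. Country may already absorb some of the schooling differences. cUHDRS also contains TFC and TMS, so its education share may lie towards the low end. Age, CAG and CAP already overlap, and the protocol warns of multicollinearity. These are reasons to add one term only. There is no worked case in the documents for sex as a main covariate.

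None of this removes the gain from one education term in models that have no baseline score.

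**Conclusion.** The point holds for the two X & Y=BSL clinical-endpoint rows, for SDMT, SWR and cUHDRS. Under the assumptions stated (n = 92, 10 base parameters, education R² of 5-20%), one education term would lower the slope's SE by about 2-10%. It would also guard against a shift of about one fifth of the slope in the illustrated case. If education does not matter, intervals widen by under 1%, or by about 3% if it still correlates 0.2 with the predictor.

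For the change rows the gain in precision is negligible to small. The reason to look there is robustness, and a sensitivity analysis is enough.

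This is a low-priority improvement. Every analysis is declared exploratory with no formal hypothesis testing (SAP Section 4), and the primary prognostic models are not the ones materially affected.

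**What to change.** - In Table 3, add education level as one ordered term (1 df) to the X & Y=BSL rows for SDMT, SWR and cUHDRS, for X=mHTT and X=CSF biomarkers. Report the slope with and without it.
- For the 15-month change rows, state in SAP 4.5.2.2 that the protocol's optional gender-and-education model will be run as a sensitivity analysis, shown beside the main slope. Sex is not needed as a main covariate.

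Both changes need only SAP wording and variables already collected. The statistical cost is 1 df in the 12 baseline models. Fixing the choice before results are seen also prevents selective use of an optional adjustment.

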2.2 SECONDARY OBJECTIVE

The secondary objective of this study is to investigate the temporal profile of longitudinal CSF mHTT changes within patient, and the association of these changes with corresponding changes in biomarkers of neuronal injury (e.g., CSF NfL and tau) and clinical outcomes using the following endpoints:

- Within-patient change from baseline in CSF mHTT levels at 3, 9, and 15 months
- Association of change from baseline in CSF mHTT levels at 3, 9, and 15 months and:
 - Change from baseline in clinical measures (cUHDRS, TFC, TMS, SDMT, SWR, and IS) at 3, 9, and 15 months
 - Change from baseline in biomarkers of neuronal injury (e.g., CSF NfL and tau) at 3, 9, and 15 months
 - Change from baseline in brain atrophy endpoints, as determined by brain MRI at 3, 9, and 15 months

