6.4 SECONDARY ANALYSES

The secondary objective for this study is to investigate the within-patient change from baseline in CSF mHTT levels and the association between changes from baseline in CSF mHTT levels at 3, 9, and 15 months and changes in clinical measures (cUHDRS, TFC, TMS, SDMT, SWR, and IS), biomarkers of neuronal injury, and brain atrophy endpoints.

Initially, a linear model will be used to evaluate the association between each response variable (e.g., change from baseline to 15 months in CSF NfL levels) and the change in CSF mHTT level, without adjustment for any baseline characteristics. A similar model will then be considered, adjusting for baseline level of the response variable, CAG, and baseline CAP. A sensitivity analysis to evaluate the impact of additional baseline characteristics (e.g., baseline mHTT, gender, education level) may be performed.

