### **2.2.2 Secondary Endpoints**

The secondary objective of this study is to investigate the temporal profile of longitudinal CSF mHTT changes within patient, and the association of these changes with corresponding changes in biomarkers of neuronal injury (e.g., CSF NfL and tau) and clinical outcomes using the following endpoints:

- Within-patient change from baseline in CSF mHTT levels at 3, 9, and 15 months
- Association of change from baseline in CSF mHTT levels at 3, 9, and 15 months and:
  - Change from baseline in clinical measures (cUHDRS, TFC, TMS, SDMT, SWR, and IS) at 3, 9, and 15 months.
  - Change from baseline in biomarkers of neuronal injury (e.g., CSF NfL and tau) at 3, 9, and 15 months.
  - Change from baseline in brain atrophy endpoints, as determined by brain MRI at 3, 9, and 15 months.

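### SAP Table 3 plans no same-visit regression of clinical or BSI change on mHTT change at Months 3 and 9, although the secondary endpoint names those visits

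*SAP*

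**What the plan says.** SAP 2.2.2 gives the predictor side of the secondary endpoint as "Association of change from baseline in CSF mHTT levels at 3, 9, and 15 months and" three groups of outcomes. The clinical group reads "Change from baseline in clinical measures (cUHDRS, TFC, TMS, SDMT, SWR, and IS) at 3, 9, and 15 months" and the imaging group "Change from baseline in brain atrophy endpoints, as determined by brain MRI at 3, 9, and 15 months". The objective in Protocol 2.2, repeated in the SAP, speaks of "the association of these changes with corresponding changes in biomarkers of neuronal injury (e.g., CSF NfL and tau) and clinical outcomes".

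SAP 4.5.2.2 says that the models relate a response to a main predictor at a given time point, and refers to Table 3 for the full list. In Table 3:

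- The row for mHTT change against clinical change has the time points "X=3M, 9M, 15M, Y=15M"; with its covariates the entry reads "X=3M, 9M, 15M, Y=15M BSL- Clin.endp, BSL-mHTT, BSL-Age, CAG, CAP, Country".
- The row for mHTT change against BSI percentage change has "X=3M, 9M, 15M, Y=15M BSL-mHTT, BSL-Age, CAG, CAP".
- The row for mHTT change against CSF biomarker change puts X and Y together at 3, 9 and 15 months.
- A further BSI row takes the outcome at 3, 9 and 15 months, but its predictor is baseline mHTT, not change in mHTT.

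**The concern.** The table has one notation for same-visit pairing, used in the CSF biomarker row, and another for an outcome fixed at Month 15, used in the clinical and BSI rows. Taken as written, the clinical and BSI rows answer the secondary question at Month 15 only. At Months 3 and 9 they ask something else: whether an early change in mHTT is related to a later, longer change in the outcome.

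That is a reasonable question, but it is not the one SAP 2.2.2 sets out. Part of a stated secondary endpoint thus has no planned model. The clinical and imaging slopes at Months 3 and 9 would also not be like-for-like with the biomarker slopes at those visits. If same-visit results are wanted later, they would have to be added after the plan was final.

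**Working it through.** The documents give no figure to reproduce here, since the point rests on no power or error-rate calculation. The check is a count of model pairs and a comparison of intervals.

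**Inputs**
- Visits: Months 3, 9 and 15 (SAP 2.2.2), which are Days 85, 253 and 421 (Protocol Appendix 1).
- Clinical endpoints in Table 3: cUHDRS, TFC, TMS, SDMT and SWR, so 5.
- BSI measures (SAP 4.5.1.5): ventricular, caudate and whole brain, so 3.
- CSF biomarkers in Table 3: NfL, tau and YKL-40, so 3.

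**Count of mHTT change-on-change models**

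Same-visit pairs implied = outcomes x 3 visits. With Y fixed at Month 15, each outcome gets one same-visit model (X at Month 15) and two lagged models (X at Months 3 and 9).

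| Outcome group | Same-visit pairs implied | Planned | Absent (Months 3 and 9) | Lagged models planned |
|---|---|---|---|---|
| Clinical (5) | 5 x 3 = 15 | 5 | 10 | 10 |
| BSI (3) | 3 x 3 = 9 | 3 | 6 | 6 |
| CSF biomarkers (3) | 3 x 3 = 9 | 9 | 0 | 0 |

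Absent in total: 10 + 6 = 16.

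**How far the lagged models are from same-visit**

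Intervals from Day 1 are 85 - 1 = 84, 253 - 1 = 252 and 421 - 1 = 420 days.

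- Month 3 predictor, Month 15 outcome: (420 - 84) / 420 = 336 / 420 = 80% of the outcome interval lies after the predictor window.
- Month 9 predictor, Month 15 outcome: (420 - 252) / 420 = 168 / 420 = 40%.

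These shares start the outcome clock at Day 1. Baseline MRI is taken at screening, and SAP 4.4 takes the first available pre-puncture measure as clinical baseline, so the outcome interval may begin earlier. With a start at Day -29, the first day of the screening period, it is 420 + 29 = 449 days, and the shares become 336 / 449 = 75% and 168 / 449 = 37%. The picture does not change.

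**Whether anything else supplies the 16 models**
- SAP 4.5.2.1 plans scatter plots at each time point, but these are descriptive and take their pairs from Table 3.
- SAP 4.5.2.2 allows unlisted analyses only to understand a safety concern.
- SAP 4.5.3 allows further exploratory analyses without naming any.
- The Table 3 footnote and SAP 4.9 allow an interim analysis on data up to, for example, 9 months, but it is optional.

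None of these commits to the models.

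**The case against.** The best defence is that fixing the outcome at Month 15 is deliberate and sensible. Protocol 3.3.1 expects clinical decline to be measurable over a year or more, so a Month 3 clinical change may be mostly noise. An early mHTT change set against a later outcome also suits the study's interest in the causal pathway. The primary endpoints list the same three visits, while Protocol 6.3 names only the change to 15 months, so a visit list does not always mean a regression at each visit. Everything is exploratory, and 16 more models add unadjusted p-values.

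Much of this stands as a reason to keep the lagged models. It does not remove the mismatch. The SAP gives no reason for dropping the early visits, and it does use them for biomarker change and for BSI against baseline mHTT.

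Four stronger readings are tempting but not supported:

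- *Months 3 and 9 go unanalysed for clinical and imaging outcomes.* They do not. SAP 4.5.1 and Table 2 give descriptive and MMRM outputs for cUHDRS, its components and BSI at all available visits. BSI at those visits is modelled on baseline mHTT, and the early mHTT changes serve as predictors.
- *Both sets of lagged models concern mainly the later period.* This is true for Month 3 (80%) but not for Month 9 (40%).
- *Readers will take the lagged slopes for same-visit associations.* The table cell states the X and Y visits separately, so the lag is open to view.
- *Table 3 contradicts Protocol 6.4.* That section plans the "association between changes from baseline in CSF mHTT levels at 3, 9, and 15 months and changes in clinical measures" and attaches no visit to the clinical or MRI change; its only worked example is at 15 months. The word corresponding in the objective is also attached to biomarkers and clinical outcomes, with MRI appearing only in the endpoint list. The conflict is within the SAP, between 2.2.2 and Table 3.

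**Conclusion.** The point holds, within limits. For clinical endpoints and BSI, the planned regressions include no same-visit association of mHTT change with outcome change at Months 3 and 9, although SAP 2.2.2 names those visits. The gap is 16 models: 10 clinical and 6 BSI. Month 15 is covered for both groups and CSF biomarkers at every visit, so the secondary endpoint is only partly unaddressed.

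The count assumes that Table 3 is exhaustive, as SAP 4.5.2.2 describes it, and that its two notations are meant to differ. It leaves out the Independence Scale, which the endpoint names but Table 3 omits at every visit; that is a separate matter. It also leaves out the rows with CSF biomarkers as predictor, which carry the same time-point cell but are not part of this mHTT endpoint. The 80% and 40% shares assume nominal visit days.

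There is no error-rate consequence, because no hypothesis is formally tested. What is at stake is whether a stated secondary endpoint is answered by a planned analysis. The two SAP passages should be reconciled before the final analysis.

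**What to change.** In the two mHTT-change rows of Table 3 (clinical endpoints and BSI), add pairing of X and Y at the same visit for 3, 9 and 15 months, in the notation of the CSF biomarker row. Keep Month 3 and Month 9 mHTT change against Month 15 outcome as separate models, labelled lagged and exploratory. Same-visit models then rise from 5 to 15 for the clinical endpoints and from 3 to 9 for BSI.

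The cost is two table cells and about 16 further regressions. CSF, clinical and MRI assessments are already scheduled at these visits (Protocol Appendix 1), so no new data are needed. The downside is 16 more unadjusted p-values, which should be read as descriptive.

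If the sponsor wants Month 15 outcomes only, the alternative is to restate the secondary endpoint in SAP 2.2.2 to match Table 3.

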##### **4.5.1 Longitudinal Changes over Time**

The objective of this section is to describe the longitudinal changes over time, to understand disease progression, for all different clinical, digital and PD endpoints, while adjusting for known prognostic factors (such as CAG repeats). Data outside a time window of +- 56 days from the expected scheduled visit will not be used for analysis of summary tables and mean plots by visit.

For the primary and secondary endpoints descriptive tables will be used to summarize the different variables on absolute value, change from baseline and percentage change (where appropriate) from baseline by visit.

For continuous variables, spaghetti plots showing patient profiles and boxplots across time will be presented.

Where the numeric variable indicates an ordinal, rather than continuous, outcome, the analysis will focus on frequency counts and percentages by visit; no other summary statistics will be provided.

In order to model the change from baseline on each individual continuous parameter across time, a mixed-model repeated measures (MMRM) analysis will be applied. This model will include as covariates the baseline parameter, number of CAG repeats, baseline age, CAP, country (as categorical, only for outcome assessments [patient-, observer- and clinician-reported, and performance]) and time (as categorical). Data outside a time window of +- 56 days from the expected scheduled visit will not be used for this analysis. Estimates for the change from baseline based on the MMRM model, at each time-point and computed for the baseline average value of the other baseline covariate, along with corresponding standard error, 95% CI and unadjusted p-value will be presented. Technical details of the MMRM model (e.g. methods for the denominator degree of freedom, variance-covariance matrix, etc.) are given in [Appendix 3](#).

Although confidence intervals and p-values will be reported, no formal hypothesis testing will be considered.

A detailed list of outputs produced for each parameter for describing the longitudinal change over time is described in [Table 2](#).

The procedure that will be used to fit mixed-models in SAS is as follows (with Day 421 as example):

```
proc mixed data=dataname plots=all;
class subjid time Country;
model y-variable=Baseline_y-variable + CAG + CAP + Baseline_Age + Country + time;
repeated time / subject= subjid type=UN;
Estimate "Day 421"
  Intercept 1
  Baseline_y-variable &BASEY
  CAG &CAGBL

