#### **4.5.1.5 MRI Volumes and Boundary Shift Integrals**

A 3D T1-weighted structural MRI scan will be used to quantitate whole brain, caudate and intraventricular volumes. The only absolute measures are the structural volumes (baseline), while boundary shift integral (BSI) are used to assess changes in volumes over time. Three boundary shift integrals will be considered: K-means ventricular boundary shift integral (VBSI), K-means caudate boundary shift integral (CBSI) and K-means brain boundary shift integral (KNBBSI). To be noticed is that BSI values represent already a measure of change from baseline.

The affine scaling factor will be used for normalizing volumetric imaging values (both absolute volumes and BSI), in order to remove the confounding influences of the head size of the patients. Normalized versions are derived as follow:

$$\text{VOLn} = \text{VOL} / \text{ASF}$$

$$\text{BSIn} = \text{BSI} / \text{ASF}$$

where ASF= Affine Scaling Factor and VOL= absolute structural volumes

Normalization is not required for BSI percent change from baseline (or annualized percent change) given that:

$$\text{BSI\_percent-change} = \text{BSI} / \text{VOL} * 100 = \text{BSIn} / \text{VOLn} * 100$$

Only data with a QC flag equals to 'Pass' will be used in the analyses.

Descriptive tables and plots as well results from the MMRM model will be provided as described in Section 4.5.1 and [Table 2](#).

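### SAP Table 3 leaves baseline volume out of the BSI models, although every other mHTT change model it specifies adjusts for the baseline level of the response

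*SAP*

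**What the plan says.** **Protocol.** Section 6.3 lists brain imaging among the primary responses and specifies a second model "adjusting for baseline level of the response variable (e.g., baseline cUHDRS), baseline CSF mHTT levels, CAG, and baseline CAP". Section 6.4 covers change in mHTT against clinical, biomarker and brain atrophy changes, with a model "adjusting for baseline level of the response variable, CAG, and baseline CAP". SAP Appendix 1 reprints the 6.3 rule with MRI still in the list.

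**SAP Table 3.** For baseline mHTT against change in clinical endpoints the covariates are "BSL- Clin.endp, BSL-Age, CAG, CAP, Country", so the baseline response is in the model. The CSF biomarker rows also carry their own baseline. For BSI, expressed as percent change, there are three rows:

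- Baseline mHTT ("X=BSL, Y=3M, 9M, 15M"), which serves the primary objective: baseline age, CAG and CAP only.
- Change in mHTT, which serves the secondary objective: "BSL-mHTT, BSL-Age, CAG, CAP". The same string also sits inside the clinical and CSF biomarker change rows, but there the baseline response precedes it.
- Change in CSF biomarker: baseline biomarker, baseline age, CAG and CAP.

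**SAP 4.5.1.5.** "The only absolute measures are the structural volumes (baseline), while boundary shift integral (BSI) are used to assess changes in volumes over time". Percent change is defined as BSI divided by baseline volume, times 100.

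**SAP 4.5.1 and Table 2.** Table 2 marks BSI and normalised BSI for MMRM. Of that model the SAP says: "This model will include as covariates the baseline parameter, number of CAG repeats, baseline age, CAP".

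**The concern.** Imaging is one of the three primary outcome families, and its mHTT models are adjusted differently from the other two without explanation. Baseline volume is a marker of how far the disease has already gone. The protocol reports that CSF mHTT correlates with disease burden in cross-sectional studies (1.2) and that whole brain, caudate and ventricular volumes predict and track decline (3.3.3.5). The SAP itself plans to model baseline mHTT against normalised baseline volume.

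If mHTT is related to baseline volume, and percent loss depends on baseline volume, the mHTT slope for BSI mixes prediction of future loss with atrophy already present. The direction could also differ between measures. If higher mHTT goes with more atrophy, a smaller brain or caudate denominator raises percent loss, while a larger ventricular denominator lowers percent expansion. The three BSI results could then disagree for arithmetic reasons.

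The MMRM raises a practical problem as well. Its code calls for a baseline value of the response, and a programmer fitting BSI would have to guess what to supply.

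**Working it through.** The plan gives no figure that depends on this covariate, so there is nothing of its own to reproduce. The check compares the rows, then asks whether percent change makes the covariate redundant.

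**1. Change models in Table 3 with mHTT as predictor**

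| Response | Predictor | Baseline of response in model? |
|---|---|---|
| Clinical (cUHDRS, TFC, TMS, SDMT, SWR) | baseline mHTT | yes |
| Clinical | change in mHTT | yes |
| CSF biomarkers | baseline mHTT | yes |
| CSF biomarkers | change in mHTT | yes |
| BSI, percent change | baseline mHTT | no |
| BSI, percent change | change in mHTT | no |

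**2. What dividing by baseline volume does.** The SAP identity is BSI/VOL × 100 = BSIn/VOLn × 100, where both normalised quantities are divided by the affine scaling factor (ASF). With illustrative values BSI = 0.2, VOL = 5.0 and ASF = 1.3, both sides equal 4.0. Head size cancels.

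Dependence on volume is a separate matter. Suppose absolute loss varies as volume to the power k. Percent loss then varies as volume to the power k − 1, which is free of volume only when k = 1, that is, when loss is proportional to volume.

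**3. Illustration under assumed inputs (none from the documents).** Mean loss 4%, coefficient of variation of loss 40%, coefficient of variation of baseline volume (CV) 10% or 20%, correlation ρ of mHTT with volume 0 to −0.6 given age and CAG, n = 90, no true mHTT effect, 4,000 runs per setting.

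To first order, the spurious slope per SD of mHTT is mean loss × (k − 1) × CV × ρ. For k = 0 (absolute loss unrelated to volume):

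- CV 10%, ρ = −0.2: 4 × (−1) × 0.1 × (−0.2) = 0.08 percentage points.
- CV 20%, ρ = −0.6: 4 × (−1) × 0.2 × (−0.6) = 0.48 percentage points.

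Simulated slopes without baseline volume were 0.087 and 0.549 in these two settings; the first-order formula ignores the curvature of 1/volume. Over ρ from −0.2 to −0.6, the 95% CI excluded zero in 7% to 74% of runs. With baseline volume added, the slope was within 0.004 of zero and the rate was 4.4% to 5.0%.

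When loss was proportional to volume (k = 1), or ρ was 0, both models gave slopes near zero and rates of 4.5% to 6.0%. So percent change does not in general replace the covariate, but the effect can be nil.

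**4. Precision.** Adding volume multiplies the standard error of the mHTT slope by about √(1 − r²)/√(1 − ρ²). Here r is the correlation of volume with the response and ρ that of volume with mHTT, both conditional on the covariates already in the model. On assumed values:

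- r = 0.5, ρ = 0.2: 0.866/0.980 = 0.88, a gain.
- r = 0.4, ρ = 0.4: 1.00, no change.
- r = 0.3, ρ = 0.4 in absolute value: 0.954/0.917 = 1.04, a small loss.

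**The case against.** The strongest reply is that the protocol rule does not carry over directly to BSI. BSI is already a change measure and has no baseline level of its own. It is not formed by subtracting a baseline score, so baseline measurement error does not enter it as it does for cUHDRS or NfL, and baseline volume is already the denominator. These differences are real. They weaken the analogy but do not dispose of it, because the denominator settles the matter only if loss is proportional to volume, and the SAP neither claims nor plans to check that.

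A second reply is that atrophy may be a consequence of mHTT, which the protocol treats as the assumed disease-causing protein. Adjusting for volume would then remove part of what a prognostic slope should show. This also stands in part: the slopes with and without volume answer different questions. But the same argument applies to baseline cUHDRS and NfL, for which the plan does adjust. It is a reason to report both slopes.

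Third, the SAP takes precedence over the protocol where specified, the outcome families already differ in other covariates and transformations, and further exploratory analyses are allowed. All true. Precedence means, however, that Table 3 as written would govern, and it gives no reason for the omission.

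A reader might also infer that every other primary outcome is adjusted for its baseline. The documents do not support that. The Independence Scale is a primary endpoint with no Table 3 model, and plasma NfL is not modelled on mHTT. The statement holds for the mHTT change models that Table 3 does specify.

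**Conclusion.** The omission is plain from the text. All BSI rows of Table 3 leave out baseline volume, Protocol 6.3 and 6.4 call for the baseline level of the response, and no reason is given. Separately, the baseline parameter for the BSI MMRM is undefined.

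The consequence is conditional. The mHTT slope reflects existing atrophy only if percent loss depends on baseline volume and mHTT is related to baseline volume after allowing for age, CAG and CAP. The documents give neither relationship, so the size is unknown and may be nil. The simulation shows only that the mechanism can operate.

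A reader might infer that the planned BSI slopes are confounded, or that precision is being thrown away. Neither is shown: the first depends on unmeasured relationships and on which question the slope is meant to answer, and the second can go either way. Nor is this a matter of error control, since both documents call all analyses exploratory with no predefined hypothesis testing. It is an inexpensive improvement in consistency and interpretability.

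**What to change.** - In SAP Table 3, add the matching head-size-normalised baseline volume (whole brain, caudate or ventricular) to the additional covariates of all BSI rows, including the CSF-biomarker row.
- Report the slope of the main predictor with and without that covariate, and say that the two answer different questions.
- In SAP 4.5.1 or 4.5.1.5, name the same volume as the baseline parameter for the BSI MMRM.

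If the sponsor prefers to keep the rows as they are, the SAP should state why percent change makes the covariate unnecessary; the MMRM definition is still needed.

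The cost is SAP wording and one more covariate per model. The normalised baseline volumes are already derived under 4.5.1.5, so no new data are required. The interval for the mHTT slope may be slightly wider if mHTT and volume are correlated.
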